11.1.6. Other outcomes

Overall Survival: Overall Survival (OS) is defined as the time from enrollment to death due to any cause, or censored at date last known alive.

Progression-Free Survival: Progression-Free Survival (PFS) is defined as the time from enrollment to the earlier of progression of radiated lesions or death due to any cause. Participants alive without disease progression in radiated lesions are censored at date of last disease evaluation.

Time to Progression: Time to Progression (TTP) is defined as the time from enrollment to progression of radiated lesions, or censoring at date of last disease evaluation for those without progression reported.

11.1.7. Response/Recurrence Review

The study PI will make all final determinations of response, progression, and recurrence. For patients requiring whole brain radiation as salvage therapy, irradiated lesions will be censored for all response and recurrence-based outcomes at the point of the preceding imaging assessment.

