Brainstem (defined as brainstem volume, inclusive of upper spinal cord, minus GTV)	Dose to 0.035cc ≤28 Gy	If dose to 0.035cc >28 Gy, undercover PTV while maintaining 100% GTV coverage. If not achievable, dose reduce GTV to highest dose which meets brainstem constraint, through 23 Gy in 5 fractions. 100% of GTV should always receive at least 23 Gy in such a scenario.

*Inclusive of dose imparted by stereotactic radiosurgery if patient received stereotactic radiosurgery and stereotactic radiotherapy; normal tissue constraints pertain only to the radiotherapeutic treatment course delivered on protocol.

Management of radiation dose to the patient from daily localization

Cone beam CT or stereoscopic KV imaging will be used in this study. The doses used for daily localization images are extremely low. MV imaging (which deposits a markedly greater radiation dose) will not be employed in this study.

Future radiation considerations

For patients with progressive intracranial disease (e.g. local recurrence, distant intracranial failure), stereotactic radiation approaches will be favored over whole brain radiation. In settings of leptomeningeal disease or overwhelming distant intracranial failure with lack of viable systemic therapy, whole brain radiation will be considered/utilized.

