11.1.5. Local recurrence at the individual metastasis level

Definition of local recurrence: Local recurrence (PD in a radiated metastasis) at the individual metastasis level represents the primary endpoint of the study and will be measured from the date of enrollment to the first date that recurrent or progressive disease is objectively documented (taking as reference for progressive disease the smallest measurements recorded since the treatment started). For lesions ≥ 10 mm in largest unidimensional size at post-radiation nadir, a 20% increase in diameter will constitute a local recurrence. Lesions < 10 mm in maximal unidimensional size prior to PD must display 2-3mm of definitive progression to be considered to have displayed a local recurrence. Metastases that enlarge by $< 20\%$ but which are treated with definitive local

therapy (for example, a metastasis that increases from 21mm to 25mm, at which point a craniotomy is performed) will be right-censored. Enlargement due to radiation necrosis as determined by the Study PI will not count as progression. The study PI (blinded to treatment assignment per the above procedures) will make the delineation of local recurrence versus not.

As a sensitivity analysis, metastases considered to have displayed a local recurrence prompting salvage therapy but not meeting criteria for radiographic PD (for example, a metastasis that increases from 21mm to 25mm, at which point a craniotomy is performed) will be treated as a local recurrence on the date that salvage therapy is initiated.

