13.7.2. Evaluation of the Primary Efficacy Endpoint

All analyses will be intent-to-treat.

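### The whole-brain-radiation censoring rule in section 11.1.7 has no exception for lesions that already meet local recurrence, and so conflicts with the primary endpoint definition in section 11.1.5

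*Protocol*

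**What the plan says.** Section 11.1.5 defines the primary endpoint, local recurrence of an individual metastasis, which "will be measured from the date of enrollment to the first date that recurrent or progressive disease is objectively documented". It has one censoring rule for salvage, and that rule is conditional. It begins "Metastases that enlarge by $< 20\%$ but which are treated with definitive local" and right-censors lesions treated with local therapy before they reach the threshold. Lesions that reach the threshold are outside it and remain events. A sensitivity analysis in the same section takes recurrences that prompt salvage without meeting radiographic progression; each "will be treated as a local recurrence on the date that salvage therapy is initiated".

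Section 11.1.7 adds a second rule for patients whose salvage is WBRT: "irradiated lesions will be censored for all response and recurrence-based outcomes at the point of the preceding imaging assessment". It sets no condition on the state of the lesion.

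Section 11.1.6 defines progression-free survival (PFS) for the participant, as "the time from enrollment to the earlier of progression of radiated lesions or death due to any cause", and adds: "Participants alive without disease progression in radiated lesions are censored at date of last disease evaluation".

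Section 5.8 says when WBRT is expected: "In settings of leptomeningeal disease or overwhelming distant intracranial failure with lack of viable systemic therapy, whole brain radiation will be considered/utilized". For other intracranial progression, including local recurrence, it favours stereotactic treatment.

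**The concern.** Sections 11.1.5 and 11.1.7 give different answers for the same lesion. If a radiated metastasis first meets the recurrence criteria on the scan that leads to WBRT, section 11.1.5 records an event on that date and section 11.1.7 records a censored observation. Which one applies decides whether a primary endpoint event is counted.

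The censoring is also unlikely to be neutral. WBRT is kept for leptomeningeal disease or overwhelming distant failure, so the rule acts on patients with a poor intracranial course. Section 13.5 analyses the endpoint with Kaplan-Meier curves, the log-rank test and Cox regression for clustered data, all of which assume that censoring carries no information about recurrence. If documented recurrences are removed at different rates in the two arms, the treatment comparison shifts. Additional radiotherapy after the first course, WBRT included, is itself compared between arms (secondary objective 10).

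**Working it through.** **1. The passages side by side.** Take a lesion with no recurrence on scan k−1 that first meets section 11.1.5 on scan k. Scan k prompts WBRT.

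| Meaning of *preceding* in 11.1.7 | Censoring date | Event date under 11.1.5 | Result |
|---|---|---|---|
| Last scan before WBRT | scan k | scan k | Same date; the text orders censoring and does not say that the event prevails |
| Scan before the prompting scan | scan k−1 | scan k | Event falls after censoring and is lost |

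A recurrence dated before the censoring scan is not in doubt in practice, since the event comes first, although section 11.1.7 does not say so.

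**2. The plan's own figure.** Inputs from section 13.1: control recurrence 27.5% at one year, HR 0.60, one-sided alpha 0.10, power 90%, accrual 2.8 years, minimum follow-up 6 months, inflation of 20% and 33%.

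- Freedman's formula gives 106 events.
- With exponential times and uniform accrual, the event probability is 0.439 (control) and 0.298 (AGuIX), mean 0.369, so 106 / 0.3686 = 287.6 lesions.
- 287.6 / 0.80 × 1.33 = 478, against 474 stated (0.9% apart).

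The sample size is reproduced, and this point does not affect it.

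**3. How many lesions might be affected.** The protocol gives no WBRT rate, so only a conditional figure is possible. Assume that 10% of patients receive WBRT (about 47 of 474 lesions), that all their lesions are still at risk, and that these lesions recur at the design rates.

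| Interval ending at the prompting scan | Control | AGuIX (HR 0.60) | Mean | Of 47 lesions |
|---|---|---|---|---|
| 2 months | 1 − 0.725^(1/6) = 5.2% | 1 − 0.725^(0.6/6) = 3.2% | 4.2% | about 2 |
| 3 months | 1 − 0.725^(1/4) = 7.7% | 1 − 0.725^(0.6/4) = 4.7% | 6.2% | about 3 |

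These intervals are within the 1.5- to 3-month scan spacing in section 10. For comparison, the design rates imply 27.5% and 1 − 0.725^0.6 = 17.5% at one year, mean 22.5%, or about 107 of 474 lesions before deaths are allowed for. Two to three lesions are about 2% to 3% of that. If local and distant failure cluster, the number is higher; the protocol gives no basis for saying by how much.

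**4. What a given loss would do.** The share lost is an assumption here. Power = Φ(½√D × |ln 0.60| − 1.2816), starting from Schoenfeld's D = 101.

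| Share of recurrences lost, both arms | Events left | Power |
|---|---|---|
| 0% | 101 | 90.1% |
| 5% | 96 | 88.9% |
| 10% | 91 | 87.6% |
| 20% | 81 | 84.5% |

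Unequal loss moves the estimate. As a rough event ratio, losing 20% of control and 10% of AGuIX recurrences gives 0.60 × 0.90 / 0.80 = 0.675; the reverse gives 0.60 × 0.80 / 0.90 = 0.533. These show direction and sensitivity. They are not forecasts.

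**The case against.** The strongest reply is that the natural meaning of the preceding scan is the last one before WBRT, which is normally the prompting scan. Event and censoring then share a date, the usual convention places events ahead of censoring, and the recurrence is kept. Such detail is often left to a statistical analysis plan, which is not shown here. Censoring lesions that have not recurred when WBRT starts is also an ordinary choice. Much of this stands: on that reading a programmer following convention would lose nothing. It does not remove the point, because section 11.1.7 itself orders censoring without condition, the other reading is open, and section 11.1.5 shows that where the authors wanted salvage censoring limited to lesions below the threshold, they said so.

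Three stronger readings are tempting, and the protocol does not support them.

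- A reader might infer that deaths after WBRT drop out of PFS. Section 11.1.7 speaks of lesions and of response and recurrence, and names neither PFS nor death. Section 11.1.6 counts death from any cause and censors only participants who are alive. Deaths would be lost only if PFS were classed as recurrence-based, which would contradict section 11.1.6.
- A reader might infer that the rule defeats the sensitivity analysis in section 11.1.5. That analysis covers only lesions below the progression threshold, with craniotomy as the example. Given section 5.8, WBRT prompted by such a lesion should be rare. The two rules do give different answers for that case, so it needs a sentence.
- A reader might infer that a large share of recurrences is at stake. That needs a single-scan recurrence risk well above what the protocol's annual rate implies.

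**Conclusion.** Wrong as written, and minor. Section 11.1.7 can turn a documented primary endpoint event into a censored observation, against section 11.1.5. Under one meaning of the preceding scan the event is lost; under the other its status is unresolved in the text, and convention would probably keep it.

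The size cannot be computed without a WBRT rate. The figure of 2 to 3 lesions for every 10% of patients given WBRT assumes that their lesions recur at the average design rate, so it is too low if local recurrence coincides with overwhelming distant failure. Equal loss of that order would cost little power. The main reason to settle the rule is that the choice affects event status in the primary analysis and should not be left open until the data are in hand.

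**What to change.** Amend section 11.1.7 to say that:

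1. The scan meant is the last imaging assessment before WBRT starts.
2. A lesion that meets section 11.1.5 on or before that scan is an event on the date recurrence was first documented. Only lesions without recurrence by then are censored at that scan.
3. The rule applies to lesion-level response and recurrence. Deaths after WBRT remain PFS events, as section 11.1.6 already provides.

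In section 11.1.5, add how the sensitivity analysis treats a local recurrence below the progression threshold that is salvaged with WBRT.

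The cost is a few sentences. No new data, visits or change in patient care are needed, and the sample size stands. The change should be made before treatment assignments are unblinded for analysis.

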11.2. Other Response Parameters

N/A

12. DATA REPORTING / REGULATORY REQUIREMENTS

Adverse event lists, guidelines, and instructions for AE reporting can be found in Section 7.0 (Adverse Events: List and Reporting Requirements).

12.1. Data Reporting

12.1.1. Method

The Office of Data Quality (ODQ) will collect, manage, and perform quality checks on the data for this study.

12.1.2. Responsibility for Data Submission

Investigative sites within DF/HCC or DF/PCC are responsible for submitting data and/or data forms to the Office of Data Quality (ODQ) in accordance with DF/HCC policies.

12.2. Data Safety Monitoring

The DF/HCC Data and Safety Monitoring Board (DSMB) will review and monitor study progress, toxicity, safety and other data from this study. The Board is chaired by a medical oncologist from outside of DF/HCC and its membership composed of internal and external institutional representation. Information that raises any questions about participant safety or protocol performance will be addressed by the Sponsor-Investigator, statistician and study team. Should any major concerns arise, the DSMB will offer recommendations regarding whether or not to suspend the study.

The DSMB will meet twice a year to review accrual, toxicity, response and reporting information. Information to be provided to the DSMB may include: participant accrual; treatment regimen information; all adverse events and serious adverse events reported across all sites by category; summary of any deaths on study; audit results; and a summary provided by the study team. Other information (e.g. scans, laboratory values) will be provided upon request.

12.3. Multi-Center Guidelines

N/A

12.4. Collaborative Agreements Language

N/A

13. STATISTICAL CONSIDERATIONS

13.1. Study Design/Endpoints

The primary endpoint of this study is local control on a per metastasis level. This study seeks to evaluate, in a signal-finding randomized phase II study, whether brain-directed stereotactic radiation in the presence of AGuIX nanoparticles demonstrates a signal towards improved local control relative to brain-directed stereotactic radiation alone. The study will have one phase. We will capitalize on the fact that many patients will harbor more than one intracranial tumor. Accordingly, even after accounting for intra-patient correlations, we can conduct a randomized trial with a smaller sample size than would typically be required. The study seeks to accrue 474 brain metastases from approximately 134 patients over a period of approximately 2.8 years. We plan to accrue approximately 47-48 patients per year. All patients will be followed for at least 12 months; however, the primary analysis point will be mature 6 months post the end of recruitment (in order to maintain statistical power).

We hypothesize that brain metastases will display a signal toward improved local control when managed with brain-directed stereotactic radiation and concurrent AGuIX nanoparticles as opposed to stereotactic radiation alone. In total 474 brain metastases from 134 patients would provide 90% power to detect a HR of 0.60 with radiation and AGuIX nanoparticles using a baseline local recurrence rate of 27.5% at one year (among historical controls managed with radiation alone at Brigham and Women's Hospital/Dana-Farber Cancer Institute), a one-sided type I error of 0.10, an accrual period of 2.8 years, a minimum follow up period of 6 months and 20% inflation for the competing risk of systemic death, and 33% inflation for intra-patient correlation among metastases. A stratified, correlated log rank test will be the primary method of analysis. Given this design, a final one-sided p value <0.10 in this hypothesis-generating study will suggest that a phase III randomized trial comparing brain-directed stereotactic radiation with or without AGuIX nanoparticles for patients with brain metastases is warranted.

One interim analysis for efficacy using a stratified, clustered log rank test will be conducted at 50% information time for the primary endpoint of local recurrence projected to occur roughly 6 months prior to the end of full accrual (study time 2.3 years). An O'Brien-Fleming boundary function will be used at that time to control type I error. If this rule is met, further study accrual will halt but patients already enrolled will be followed.

The randomization will be stratified as outlined below. If 2 or more potential strata could apply to a given patient, the enrolling clinician can select the stratum that is most appropriate.

13.2. Sample Size, Accrual Rate and Study Duration

As noted above, the study will enroll 474 brain metastases from approximately 134 patients. It is expected that approximately 67 patients will be randomized to each arm. The study will conclude after all protocol-specified time points have elapsed and follow up data are sufficiently mature for analysis. We estimate the study will accrue over 2.8 years.

Accrual Targets

Ethnic Category	Sex/Gender		
	Females	Males	Total
Hispanic or Latino	3	+3	=6
Not Hispanic or Latino	64	+64	=128
Ethnic Category: Total of all subjects	67 (A1)	+67 (B1)	=134 (C1)
Racial Category			
American Indian or Alaskan Native	1	+1	=2
Asian	5	+5	=10
Black or African American	8	+8	=16
Native Hawaiian or other Pacific Islander	1	+1	=2
White	52	+52	=104
Racial Category: Total of all subjects	67 (A2)	+67 (B2)	=134 (C2)
	(A1 = A2)	(B1 = B2)	(C1 = C2)

13.3. Stratification Factors

As noted above patients will be stratified into the following strata:

- Melanoma with intracranial growth consistent with tumor progression despite immunotherapy
- Gastrointestinal primary
- HER2 positive breast cancer
- Cystic metastases
- Metastases ≥ 2 cm in maximal unidimensional size
- Locally recurrent metastases after prior stereotactic radiation
- Locally recurrent metastases after prior whole brain radiation

Patients with metastases from melanoma, GI primaries, or HER2+ breast cancer, as well as those with cystic metastases or metastases ≥ 2 cm in maximal unidimensional size, who have local recurrences after prior brain-directed radiation can only be treated in the strata permitting prior radiation (last two strata above).

We will mandate that each stratum contain at least 12 patients by the end of the study in order to ensure a reasonable number of patients per stratum, with the exception of the locally recurrent metastases after prior stereotactic radiation stratum, which may be closed early if at least 12 patients have been accrued to the other strata. The treatment naïve metastases ≥ 2 cm in maximal unidimensional size stratum will target 44 patients as this stratum represents an important and prevalent brain metastasis population. No other stratum will be permitted to accrue more than 22 patients. Accrual to individual strata will be monitored as the study progresses.

13.4. Interim Monitoring Plan

Neurologic death in patients with brain metastases often is secondary to local progression of disease that has often been radiated in excess of one time. Consequently strata involving prior radiation potentially represent patients who may benefit the most from radiosensitization. However, symptomatic radiation necrosis may be more common in such cohorts given the prior treatment. Accordingly, an early stopping rule will be employed to monitor for excess toxicity in this subset of patients. If two or more of the first six patients randomized to receive AGuIX in either strata involving prior radiation (for the purposes of the early stopping rule these strata will be combined) display symptomatic radiation necrosis requiring resection within three months of treatment these strata of the study will be closed to further enrollment. Symptomatic radiation necrosis will be defined as radiographic changes consistent with necrosis in combination with predominant necrotic change seen on pathology at resection. If the true rate of symptomatic radiation necrosis requiring resection is 33%, then there is a 65% chance that at least two of the first six patients would experience such toxicity. If this early stopping rule is met, then any plans to re-open the study with a modified treatment plan will need to be formally reviewed and approved by the sponsor and by the DF/HCC SRC/IRB prior to activation. If there are less than two instances of symptomatic radiation necrosis requiring resection within the first three patients enrolled, these strata will proceed to full accrual. Case report forms in strata involving prior radiation will be monitored monthly by the unblinded CRC until either the early stopping rule is met or it is determined that the early stopping rule cannot be met.

In addition, we utilize a second early stopping rule applicable to the entire cohort. If two or more of the first six patients randomized to receive AGuIX display an acute, grade 3-5 non-hematologic toxicity within 1.5 months of the end of protocol-based treatment that is possibly, probably, or definitely related to AGuIX administration the study will be closed to further enrollment. If the true rate of such toxicity is 33%, then there is a 65% chance that at least two of the first six patients would experience it. If this early stopping rule is met, then any plans to re-open the study with a modified treatment plan will need to be formally reviewed and approved by the sponsor and by the DF/HCC SRC/IRB prior to activation. If there are less than two instances of acute, grade 3-5, non-hematologic toxicity within 1.5 months of the end of protocol-based treatment that are possibly, probably, or definitely related to AGuIX administration among the first six patients, the study will proceed to full accrual. Of note the first post-treatment assessment will occur at 1.5 months. Case report forms for such patients will be monitored weekly by the unblinded CRC until either the early stopping rule is met or it is determined that the early stopping rule cannot be met.

The study will incorporate an early stopping rule for futility. After 50% of the total patient accrual (that is, 67 of the 134 patients) have been observed through 9 months, we will evaluate the best intracranial response rate (iRR) achieved over 9 months for the pre-specified futility analysis. It is expected that the control iRR rate is on the order of 70% and the experimental iRR rate will be improved to at least 86%. Under this scenario, the overall study has 83% power for this comparison at full information (98 intracranial responses) using a one-sided 0.10 level test of proportions. For 50% information time on iRR (49 intracranial responses), it is projected that this will be reached roughly at study month 26, given an expected accrual of 47-48 patients per year, 17 months of accrual and 9 months follow-up for the first 67 patients. The Wieand rule will be used to assess futility. If the iRR is higher the experimental arm the study will proceed to full accrual. If the iRR is high in the non-experimental/placebo arm we will examine local control on

a per metastasis level before abandoning the study. If local control on a per metastasis level is also better in the non-experimental/placebo arm then the study will be abandoned. If local control is better in the experimental arm the study will proceed to full accrual. The interim analysis for efficacy based on local control is described above in section 13.1.

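### The necrosis stopping rule for the prior-radiation strata stops on the first six AGuIX patients but releases the strata on the first three patients enrolled

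*Protocol*

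**What the plan says.** All of the conflicting text is in one paragraph of Protocol section 13.4.

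- **Stop clause.** The trigger is "If two or more of the first six patients randomized to receive AGuIX in either strata involving prior radiation", with the two strata combined. If they "display symptomatic radiation necrosis requiring resection within three months of treatment these strata of the study will be closed to further enrollment".
- **Operating characteristic.** For a true rate of 33%, the protocol says "then there is a 65% chance that at least two of the first six patients would experience such toxicity".
- **Release clause.** With fewer than two instances "within the first three patients enrolled, these strata will proceed to full accrual".
- **Monitoring.** The unblinded coordinator goes through the case report forms from these strata every month, and this ends only once the boundary has been crossed or has become impossible to reach.

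The next paragraph gives a second rule, for acute grade 3-5 non-hematologic toxicity in the whole cohort. It also stops at two of the first six AGuIX patients, but its release clause keeps the same number: with fewer than two such toxicities "among the first six patients, the study will proceed to full accrual".

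**The concern.** A stopping rule needs one count that leads either to stopping or to continuing. Here the stop decision uses six patients and the release decision uses three. The release clause also says enrolled instead of randomized to AGuIX, and it drops the three-month window. If 0 or 1 of the first three patients has an event and a second event then appears among AGuIX patients four to six, the paragraph gives two opposite instructions.

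This is the only stopping rule specific to necrosis, and it covers the strata in which the protocol itself expects symptomatic necrosis may be more common. The unblinded coordinator applies it from case report forms, while the study PI and the rest of the study team are blinded (section 4.1). A rule run in that way should not depend on which sentence is read as governing. If the release sentence is followed, the 65% in the protocol no longer describes the rule in use.

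**Working it through.** **Inputs, all from section 13.4:** stop at 2 or more events in 6 AGuIX patients; release at fewer than 2 events in 3 patients; illustrative true rate 33%, taken as p = 1/3. Patients are treated as independent. The three are first taken to be the first three of the six AGuIX patients, which is the reading kindest to the protocol.

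**Step 1. Reproduce the protocol's 65%.**

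P(2 or more of 6) = 1 − (2/3)^6 − 6(1/3)(2/3)^5 = 1 − 64/729 − 192/729 = 473/729 = 64.9%. At p = 0.33 exactly it is 64.2%. The stated figure is right for six patients.

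**Step 2. The same boundary on three patients.**

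P(2 or more of 3) = 3(1/3)²(2/3) + (1/3)³ = 7/27 = 189/729 = 25.9%. The release clause is therefore satisfied with probability 1 − 0.259 = 74.1%.

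**Step 3. Probability that the clauses conflict.** Two or more events in the first three implies two or more in the first six, so the conflict probability is the difference:

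P(fewer than 2 of 3, and 2 or more of 6) = 473/729 − 189/729 = 284/729 = 39.0%.

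As a share of all cases the six-patient rule would stop: 284/473 = 60%.

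**Step 4. Other true rates.**

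| True rate | 2+ of 6 | 2+ of 3 | Conflict |
|---|---|---|---|
| 10% | 11.4% | 2.8% | 8.6% |
| 20% | 34.5% | 10.4% | 24.1% |
| 25% | 46.6% | 15.6% | 31.0% |
| 1/3 | 64.9% | 25.9% | 39.0% |
| 40% | 76.7% | 35.2% | 41.5% |
| 50% | 89.1% | 50.0% | 39.1% |

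The conflict is small when necrosis is rare and lies between 31% and 41% at rates of 25% to 50%, where the rule is meant to act.

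**Step 5. The literal reading.** If the three patients enrolled may come from either arm, the release is easier still. This needs two assumptions: 1:1 allocation (section 13.2 expects about 67 patients per arm) and a placebo event rate q, which the protocol does not give. The per-patient rate is then 0.5(1/3) + 0.5q, and the chance of two or more events in three is 7.4% at q = 0 and 12.1% at q = 10%. The finding does not depend on this reading.

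**Step 6. Exposure.** Section 13.3 says "No other stratum will be permitted to accrue more than 22 patients", and both prior-radiation strata fall under that cap. That gives at most 2 × 22 = 44 patients, about 22 of them on AGuIX at equal allocation, so at most about 22 − 6 = 16 AGuIX patients beyond the first six.

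**The case against.** The best defence is that this is a slip which the paragraph largely repairs. The stop clause is unconditional, the 65% is for six, and the parallel rule says six. Monthly review continues until the rule is met or cannot be met, and 0 or 1 event in three patients settles neither. Proceeding to full accrual could then mean only that enrolment goes on while the six-patient boundary stays live.

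The inference about intent is sound, and it shows which way to correct the text. It does not make the release sentence harmless. The rule states no accrual pause, so a sentence that merely allowed enrolment to continue would have no function. In the parallel rule the same phrase is the final outcome once the boundary has not been reached.

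Other parts of the defence stand:

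- The 39% is conditional on a true rate of one third, which the protocol uses to illustrate the rule and does not predict. Necrosis requiring resection within three months is a narrow event, and at a 10% rate the conflict is 8.6%.
- The parallel release clause also leaves the arm unnamed, so the missing AGuIX restriction may be shorthand. The number three is the main defect.
- Sixteen patients is an upper bound. The prior-stereotactic stratum may close early. With no accrual pause, some patients would enrol during the observation window even under a corrected rule.
- The DSMB still reviews toxicity twice a year (section 12.2).

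**Conclusion.** The concern holds. The stop and release clauses of the necrosis rule contradict each other in current, operative text. At the protocol's illustrative rate, and counting the three as AGuIX patients, they give opposite instructions in 39.0% of cases. If the release sentence governed, the stopping probability would be 25.9% against the stated 65%. These figures assume independent patients and a true rate of one third; at rates of 25% to 50% the conflict is 31% to 41%, and at lower rates it is smaller.

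The consequence is limited to safety monitoring in two capped strata. Sample size, power and the primary analysis are unaffected. It should still be corrected, because a safety rule should not carry two thresholds.

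**What to change.** Reword the release sentence in section 13.4 so that the strata proceed to full accrual if there are fewer than two instances of symptomatic radiation necrosis requiring resection, within three months of treatment, among the first six patients randomized to receive AGuIX in the combined prior-radiation strata. The two clauses then become complements: at a rate of one third, 64.9% stop, 35.1% proceed and none conflict. The 65% stays valid and the monitoring sentence fits.

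If three was truly intended, change the stop clause to the first three AGuIX patients and restate the 65% as about 26%.

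The cost is a one-sentence amendment, with no added patients or data.
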